1. VERSION HISTORY

Table 1. Summary of Changes

Version/ Date	Associated Protocol Amendment	Rationale	Specific Changes
1/ 08 Oct 2021	Original 23 Aug 2021	N/A	N/A
2/ 22 Feb 2022	Protocol amendment 1 08 Feb 2022	Sample size and lot consistency threshold modified in response to CBER feedback	
 Updated Section 2.2, Section 3.5.1, Section 5.1.1, and Section 5.1.2 to match the amended protocol. Updated Section 6.1.1.1.1 to reflect the modified lot consistency threshold. Updated Section 6.4 to remove subgroup analysis on primary safety endpoints.

2. INTRODUCTION

This SAP provides the detailed methodology for summary and statistical analyses of the data collected in Study C3671014. This document may modify the plans outlined in the protocol; however, any major modifications of the primary endpoint definition or its analysis will also be reflected in a formal protocol amendment.

2.1. Study Objectives, Endpoints, and Estimands

The estimands corresponding to each primary [CCI](#) objective are described in Table 2.

Table 2. Study Objectives, Endpoints, and Estimands

Objectives	Estimands	Endpoints
Primary Immunogenicity		
To demonstrate that the immune responses induced by 3 RSVpreF lots (Groups 1, 2, and 3) 1 month after vaccination are equivalent.	
 The ratio of neutralizing GMTs obtained 1 month after vaccination for every pair of RSVpreF lots (Group 1/Group 2, Group 1/Group 3, Group 2/Group 3) for RSV A and RSV B neutralization assays, in participants receiving 1 dose of study intervention and in compliance with the key protocol criteria (evaluable participants). 	
 RSV A and RSV B NTs.

PFIZER GENERAL BUSINESS

Table 2. Study Objectives, Endpoints, and Estimands

Objectives	Estimands	Endpoints
Primary Safety		
To evaluate the safety and tolerability profiles of 3 RSVpreF lots (Groups 1, 2, and 3).	
 The incidence rate of each safety outcome in participants receiving 1 dose of the study intervention, estimated by the percentage of participants reporting the event among those who receive study intervention, in the pooled RSVpreF lots and placebo. 	
 Local reactions (redness, swelling, and pain at the injection site) self-reported on e-diaries for 7 days after vaccination. Systemic events (fever, fatigue, headache, vomiting, nausea, diarrhea, muscle pain, and joint pain) self-reported on e-diaries for 7 days after vaccination. AEs from the day of consent through study completion. SAEs from the day of consent through study completion.

CC1

2.1.1. Primary Estimands

2.1.1.1. Primary Immunogenicity Estimand

The primary immunogenicity estimand will use the hypothetical strategy and compare immune responses for 3 lots of RSVpreF when the intercurrent event would not occur. In other words, the immune response is estimated in the hypothetical setting where participants follow the study schedule and protocol requirements as directed. It includes the following 5 attributes:

- Treatment condition: RSVpreF Group 1, RSVpreF Group 2, and RSVpreF Group 3.
- Population: Healthy adults 18 through 49 years of age, inclusive, as defined by the study inclusion and exclusion criteria.
- Variables: RSV A– and RSV B–neutralizing titers measured 1 month after vaccination.
- Intercurrent events: The following intercurrent events could impact the interpretation or the measurement of the immune response:
 1. The participant did not receive the study intervention as randomized.
 2. The participant did not meet the study inclusion/exclusion criteria.
 3. Major protocol violations – a protocol violation that, in the opinion of the sponsor’s study medical monitor, would materially affect assessment of immunogenicity.
 4. Blood was taken outside the window (<27 days or >42 days after RSVpreF administration).

[figure not shown]
The clinical question of interest is based on whether the immune responses for RSV A and RSV B induced by 3 lots of RSVpreF, without any influence from any other immune-modifying drugs or vaccines, measured at a homogeneous time point, are equivalent. Therefore, all data after intercurrent events, if applicable and collected, will be excluded. Major protocol violations will be determined by clinical review.

- Population-level summary: GMRs, defined as the ratio of RSV A–neutralizing GMTs for each between-lot comparison and the ratio of RSV B–neutralizing GMTs for each between-lot comparison (Group 1/Group 2, Group 1/Group 3, and Group 2/Group 3).

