1.3. Schedule of Activities

The SoA table provides an overview of the protocol visits and procedures. Refer to Study Assessments and Procedures in [Section 8](#) for detailed information on each procedure and assessment required for compliance with the protocol.

The investigator may schedule visits (unplanned visits) in addition to those listed in the SoA table, in order to conduct evaluations or assessments required to protect the well-being of the participant.

Visit Identifier	Visit 1	Visit 2
Visit Description	Vaccination	1-Month Follow-Up
Visit Window	Day 1	28 to 35 Days After Visit 1
Type of Visit	Clinic	Clinic
Obtain informed consent	X	
Obtain participant number via IRT	X	
Obtain demography and medical history data	X	
Perform clinical assessment (and physical examination and vital signs if deemed necessary)	X	
Obtain prevaccination temperature (body)	X	
Confirm negative urine (or serum) pregnancy test (for WOCBP)	X	
Discuss contraceptive use (as appropriate)	X	
Record nonstudy vaccinations	X	X
Review concomitant medication use	X	X
Review inclusion and exclusion criteria and confirm eligibility	X	
Review temporary delay criteria	X	
Obtain blood sample for antibody assessment	~20 mL ^a	~80 mL
Obtain randomization number and product kit assignment from IRT	X	
Assist with app download or issue e-diary, issue measuring device and digital thermometer; provide e-diary training	X	
Study intervention administration	X	
Postvaccination observation (30 minutes) and acute immediate reaction assessment	X	
Provide study participant with emergency contact card	X	
Review e-diary data (daily review during the 7 days following vaccination)	X	
Review e-diary for ongoing reactogenicity, obtain stop dates, collect e-diary		X
Record adverse events and serious adverse events and obtain any missing stop dates	X	X

Abbreviations: IRT = interactive response technology; WOCBP = women of childbearing potential.

a. Blood sample must be collected before vaccination.

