6.8.2. Withholding Periods for Concomitant Vaccinations and Medications

Unless considered medically necessary, the following restrictions apply to nonstudy licensed vaccines and medications as well as COVID-19 vaccines authorized for temporary or emergency use:

- COVID-19 vaccines may not be given within 14 days before or within 7 days after study intervention administration.
- Nonstudy inactivated vaccines or seasonal or pandemic influenza vaccine (whether inactivated or LAIV) may not be given within 14 days before or within 7 days after study intervention administration.
- Nonstudy live vaccines should not be given within 28 days before or within 28 days after study intervention administration.
- Systemic corticosteroids (≥ 20 mg/day of prednisone or equivalent) for ≥ 14 days should not be given within 28 days before study intervention administration through the conclusion of study participation.
- Chronic systemic treatment with known immunosuppressant medications should not be given within 60 days before study intervention administration through the conclusion of study participation.
- Monoclonal antibodies should not be given within 60 days before study intervention administration through the conclusion of study participation.
- Blood/plasma products or immunoglobulin should not be given within 60 days before study intervention administration through the conclusion of study participation.
- Prophylactic antipyretics and other pain medication to prevent symptoms associated with study intervention administration are not permitted.

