6.8.3. Permitted Nonstudy Vaccines and Medications During the Study

The following restrictions apply to permitted vaccines and medications (except when they are considered medically necessary):

- Licensed or authorized COVID-19 vaccines may be given during the study starting 7 days after study intervention administration (Day 8).
- Nonstudy inactivated vaccines and seasonal or pandemic influenza vaccine (whether inactivated or LAIV) may be given on Day 8, where Day 1 is the day of study intervention administration.

- Nonstudy live vaccines may be given starting 28 days after study intervention administration (Day 29).
- Inhaled/nebulized, intra-articular, intrabursal, or topical (eg, skin, eyes) corticosteroids are permitted. Short-term use of systemic corticosteroids (equivalent of <20 mg/day of prednisone) for <14 days prior to the administration of study intervention is permitted.
- The use of antipyretics and other pain medication to treat symptoms associated with study intervention administration is permitted.
- Medication other than that listed in [Section 6.8.1](#) and [Section 6.8.2](#) required for treatment of preexisting stable conditions is permitted.

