4. ANALYSIS SETS (POPULATIONS FOR ANALYSIS)

Data for all participants will be assessed to determine if participants meet the criteria for inclusion in each analysis population prior to unblinding and releasing the database and classifications will be documented per standard operating procedures.

Population	Description
Enrolled	All participants who sign the ICD.
Randomly assigned to study intervention	All participants who are assigned a randomization number in the IRT system.
Evaluable immunogenicity	All participants who meet the following criteria: 1. Are eligible for the study; 2. Receive the study intervention to which they were randomized at Visit 1; 3. Have a valid and determinate immunogenicity result from the blood sample collected within 27 to 42 days after vaccination; 4. Have no major protocol violations.
miITT	All randomized participants who receive study intervention and have at least 1 valid and determinate assay result after vaccination.
Safety	All randomized participants who receive study intervention.

Major protocol violations will be determined by clinical review. A major protocol violation is a protocol violation that, in the opinion of the sponsor's study medical monitor, would materially affect assessment of immunogenicity, eg, participant receipt of a prohibited vaccine or medication/treatment that might affect immune response or a medication error with suspected decrease in potency of the vaccine. The sponsor's medical monitor will identify those participants with protocol violations before any analysis is carried out.

[figure not shown]

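### Do the other vaccines permitted from Day 8 undermine the primary lot-consistency estimand?

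*SAP*

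**What the plan says.** SAP section 2.1.1.1 describes the primary immunogenicity estimand in two ways. It first sets out the hypothetical strategy: "the immune response is estimated in the hypothetical setting where participants follow the study schedule and protocol requirements as directed". After listing the intercurrent events, it explains that the question is whether the lots' responses, "without any influence from any other immune-modifying drugs or vaccines, measured at a homogeneous time point, are equivalent", and that data after intercurrent events are excluded for that reason.

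Four intercurrent events are listed: not treated as randomized, not eligible, a major protocol violation, and blood drawn outside 27 to 42 days. Receipt of another vaccine is not named. It could enter only as a major violation, for which SAP section 4 gives the example "participant receipt of a prohibited vaccine or medication/treatment that might affect immune response".

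Protocol section 6.8.3 permits licensed or authorized COVID-19 vaccines from Day 8. Of other products it says "Nonstudy inactivated vaccines and seasonal or pandemic influenza vaccine (whether inactivated or LAIV) may be given on Day 8". Read literally that is a single day, but the restriction in section 6.8.2 ends 7 days after study vaccination, so Day 8 onward is the natural reading. Live vaccines are allowed from Day 29, and the withholding periods in section 6.8.2 give way to medical necessity. Visit 2 falls "28 to 35 Days After Visit 1".

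Nonstudy vaccinations are recorded (SAP section 3.4.4) and summarized on the safety population (section 6.5.4). The supplementary immunogenicity analysis uses the mITT population (section 6.1.1.1.2).

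**The concern.** Read alone, the clinical question promises a comparison free of other vaccines, and the exclusion of data after intercurrent events is offered as the way to deliver it. The listed events do not deliver it. Someone given an influenza or COVID-19 vaccine on Day 8 has broken no rule, meets all four evaluable criteria and contributes a 1-month titer to the primary ratios. The mITT analysis keeps the same person, so comparing the two sets reveals nothing about such recipients.

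If these vaccines changed RSV titers, and if recipients were unevenly spread over lots, a lot ratio could move for a reason unrelated to manufacturing. The reported result would then answer a slightly different question from the one stated.

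**Working it through.** **Reading the definitions together.** The hypothetical setting is one in which the protocol is followed. Protocol section 9.1.1 says the same, and SAP Table 2 defines the population by compliance with key protocol criteria. A vaccine given under Protocol section 6.8.3 is compliant, so its recipient belongs in that setting. The listed events, the evaluable population and the main analysis agree with this definition. The sentence that does not fit is explanatory text beneath the list of events. The mismatch is therefore between two sentences of SAP section 2.1.1.1, and the analysis matches one of them.

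**Timing.** Day 8 is 7 days after vaccination. A draw at 28 to 35 days comes 21 to 28 days later. The analysis window of 27 to 42 days gives 20 to 35 days. The opportunity for exposure is real.

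**Model for the shift.** If a share p of a lot receives another vaccine before the draw, and that vaccine multiplies the titer by g, the mean log titer moves by p × ln(g). The ratio of lots i and j is multiplied by exp[(p_i − p_j) × ln(g)]. With equal uptake the factor is exactly 1.

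**Uptake (assumed, 5% to 20%).** The SD of the uptake difference between two lots of 225 is √[2p(1−p)/225]:
- p = 0.05: 0.021
- p = 0.10: 0.028
- p = 0.20: 0.038

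A 5-point difference is thus about 1.8 SD at 10% uptake (0.05/0.028) and 1.3 SD at 20% (0.05/0.038).

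**Effect size.** Protocol section 2.2.1 reports, for RSVpreF coadministered with Tdap, 1-month ratios of 0.97 (RSV A) and 0.96 (RSV B). Other values of g are assumptions.

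| Uptake difference | g | Factor on the lot ratio |
|---|---|---|
| 5 points | 0.96 | exp(0.05 × ln 0.96) = 0.998 |
| 20 points | 0.96 | exp(0.20 × ln 0.96) = 0.992 |
| 5 points | 0.8 to 1.25 | 0.989 to 1.011 |
| 10 points (15% v 25%) | 0.7 to 1.5 | 1.036 to 0.960 |
| 20 points (10% v 30%) | 0.7 to 1.5 | 1.074 to 0.922 |

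**Scale of the decision.** Using the protocol's SDs (section 9.5), the 95% CI half-width on the log scale is 1.965 × SD × √(2/225).
- RSV A: 1.965 × 0.96 × 0.0943 = 0.178
- RSV B: 1.965 × 1.07 × 0.0943 = 0.198

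The margin is ln(1.5) = 0.405. An observed ratio can therefore reach exp(0.405 − 0.178) = 1.26 for RSV A, or exp(0.405 − 0.198) = 1.23 for RSV B, before the criterion fails. A shift of 0.2% to 1% matters only if a ratio already lies almost on that limit.

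**Cost of excluding recipients instead.** The plan states 93.3% joint power at 225 per lot (98.5% × 94.7%). Simulating the written 95% CI rule, with zero lot difference and independent antigens, gives 87.1%. A 90% CI variant gives 94.1%, close to the stated figure. That discrepancy is a separate matter. Removing a further 10% (202 per lot) lowers the first to 79.3% and the second to 89.8%. Under either rule, exclusion costs about 4 to 8 points of power to remove a shift of about 1% or less.

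**The case for a change.** The best opposing case is that an estimand should be precise, and this one contains a sentence that its own exclusion rules do not honor. The gap is also wider than Day 8 vaccines: live vaccines from Day 29 can precede the draw, and section 6.8.2 opens with "Unless considered medically necessary, the following restrictions apply to nonstudy licensed vaccines and medications". No readable analysis isolates recipients, although the data are collected, and one extra table would be cheap. Tdap on the same day is not a COVID-19 or influenza vaccine a week or more later, so 0.96 proves nothing for those products. In an equivalence trial, one should also distrust anything that might blur a real difference.

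The wording point stands. The rest carries less weight. It could be argued that *immune-modifying* qualifies *vaccines* as well as *drugs*, so that permitted products fall outside the sentence, but the documents do not say so. The exploratory sections are redacted, so the absence of a further analysis cannot be established. The violation example in SAP section 4 is only an example, and the medical monitor judges each case before analysis. A common multiplicative effect does not blur a lot difference, because recipients of two lots keep the same ratio. Attenuation would need an effect that differs by lot, and nothing in the documents suggests one. The extra table would condition on an event after randomization and would be expected to repeat the main result.

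**Conclusion.** No change to the plan is needed. SAP section 2.1.1.1 contains a loosely worded rationale. An analyst applying the listed intercurrent events and the definition in SAP section 4 will keep recipients of permitted vaccines in the analysis, which is what a setting of protocol compliance implies. Naming the event and handling it by treatment policy would leave the analysis set, the six ratios and the decision rule as they are. Excluding recipients would cost power for no useful gain.

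The expected effect on any lot ratio is nil. A chance 5-point imbalance gives about 0.2% at the documented Tdap effect and about 1% at 0.8- to 1.25-fold. The most extreme case tried, 10% against 30% uptake with a 1.5-fold effect, gives about 8%, but that imbalance is more than five SDs under random allocation (0.20/0.038 at 20% uptake). This conclusion rests on randomized, blinded lots, on an effect that does not differ by lot, and on assumed uptake of 5% to 20%, since the documents give none. A repeat of the six ratios without recipients is a reasonable optional table, and the lot conclusion does not depend on it.

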2.1.1.2. Primary Safety Estimands

The primary safety estimands will use the treatment policy strategy and variables will be estimated regardless of whether an intercurrent event occurs.

PFIZER GENERAL BUSINESS

Reactogenicity estimands after vaccination include the following 5 attributes:

- Treatment condition: RSVpreF or placebo administered at Visit 1.
- Population: Healthy adults 18 through 49 years of age, inclusive, as defined by the study inclusion and exclusion criteria.
- Variables: Presence/absence and grade of any prespecified local reaction and systemic event within 7 days after vaccination.
- Intercurrent events: Some of the intercurrent events listed in [Section 2.1.1.1](#) may apply. However, all data collected after the intercurrent event will be included.
- Population-level summary: Percentage of participants reporting prespecified local reactions and systemic events in the pooled RSVpreF lots (Groups 1, 2, and 3) and placebo separately.

[figure not shown]
AE and SAE estimands after the day of consent have the following 5 attributes:

- Treatment condition: RSVpreF or placebo administered at Visit 1.
- Population: Healthy adults 18 through 49 years old, inclusive, as defined by the study inclusion and exclusion criteria.
- Variables: Presence/absence of AEs and SAEs reported from the day of consent through study completion (Visit 2).
- Intercurrent events: Some of the intercurrent events listed in [Section 2.1.1.1](#) may apply. However, all data collected after the intercurrent event will be included.
- Population-level summary: Percentage of participants reporting AEs and SAEs in the pooled RSVpreF lots (Groups 1, 2, and 3) and placebo separately.

2.1.2. Secondary Estimand(s)

Not applicable.

CC1

PFIZER GENERAL BUSINESS

Additional estimands defined for AEs and SAEs from the time of vaccination through study completion will use the treatment policy strategy and have similar attributes as the primary estimands defined for AEs and SAEs.

2.2. Study Design

This Phase 3, multicenter, parallel-group, placebo-controlled, randomized, double-blind study will be conducted in the US. Up to 1000 healthy women and men, 18 to \leq 49 years of age, will be enrolled. Allowing for a nonevaluable rate of approximately 10%, this will provide the required sample size of approximately 900 participants for the evaluable population analysis. Participants who withdraw or are withdrawn from the study after randomization will not be replaced, regardless of the reason for withdrawal.

There will be 4 study groups: Group 1, Group 2, Group 3 (representing 3 RSVpreF manufacturing lots), and placebo. Up to 1000 participants will be randomly assigned in a 1:1:1:1 ratio so that each group numbers approximately 250 participants.

There are 2 scheduled study visits. Participants will have blood samples for immunogenicity assessments collected both prior to vaccination (Visit 1) and 1 month after vaccination (Visit 2).

Local reactions (redness, swelling, and pain at the injection site) occurring at the RSVpreF or placebo injection site and systemic events (fever, fatigue, headache, vomiting, nausea, diarrhea, muscle pain, and joint pain) occurring within 7 days after vaccination will be prompted for and collected daily by the participant in an e-diary device or smartphone application.

AEs and SAEs will be collected from the signing of informed consent through Visit 2.

3. ENDPOINTS AND BASELINE VARIABLES: DEFINITIONS AND CONVENTIONS

3.1. Primary Endpoints

3.1.1. Primary Immunogenicity Endpoint

- RSV A- and RSV B-neutralizing titers measured 1 month after vaccination.

3.1.2. Primary Safety Endpoints

- Local reactions self-reported on e-diaries within 7 days after vaccination.
- Systemic events self-reported on e-diaries within 7 days after vaccination.
- AEs from the day of consent through study completion.
- SAEs from the day of consent through study completion.

PFIZER GENERAL BUSINESS

3.1.2.1. Local Reactions Within 7 Days After Vaccination

The local reactions reported in the e-diary are redness, swelling, and pain at the injection site, from Day 1 through Day 7 after vaccination, where Day 1 is the day of vaccination at Visit 1. This section describes derivations with details for the assessment of local reactions: any presence, maximum severity, duration, onset day of local reactions, and presence of local reactions on each and any day.

3.1.2.1.1. Presence of Local Reactions Within 7 Days After Vaccination

For the summary of the presence (yes or no) of a local reaction during the interval from Day 1 through Day 7 after vaccination, where Day 1 is the day of vaccination, the following 2 variables are derived for each participant included in the reactogenicity subset:

1. Presence (yes or no) of each local reaction on any day (Day 1 through Day 7).

The derivation is described in Table 3.

Table 3. Derived Variables for Each Local Reaction

Variable ^a	Yes (1)	No (0)	Missing (.)
Any day (Days 1-7)	The reaction is reported as “yes” with a diameter >2.0 cm for redness/swelling or “yes” for pain on any day (Days 1-7).	The reaction is reported as “no” (or “yes” with a diameter ≤2.0 cm for redness/swelling) on all 7 days or as a combination of the above and missing on all 7 days.	The participant reports the reaction as missing on all 7 days.

a. The variable will be defined for each of the 3 local reactions.

[figure not shown]
2. Presence (yes or no) of any local reaction on any day (Day 1 through Day 7).

For any local reaction on any day, a similar definition can be applied as given in Table 4.

Table 4. Derived Variables for Any Local Reaction

Variable	Yes (1)	No (0)	Missing (.)
Any day (Days 1-7)	Any reaction is reported as “yes” with a diameter >2.0 cm for redness/swelling or “yes” for pain on any day (Days 1-7).	All 3 local reactions are reported as “no” (or “yes” with a diameter ≤2.0 cm for redness/swelling) on all 7 days or as a combination of the above and missing on all 7 days.	The participant reports all local reactions as missing on all 7 days.

PFIZER GENERAL BUSINESS

